11.3.3 Locator Form

A locator form is used to obtain information to assist in finding participants through the 12-week active and follow-up phase of the study. This form collects the participant's current address, email address, and phone numbers. In order to facilitate locating participants if direct contact efforts are unsuccessful, addresses and phone numbers of family/friends who may know how to reach the

participant are collected. This information will be collected at baseline and will be updated at each contact.

No information from this form is used in data analyses, nor is this information captured in the data capture system. The locator form is stored in a secure electronic folder with other participant PHI data.

11.3.4 PhenX Substance Abuse and Addiction Core Tier 1 (PhenX Core Tier 1)

The PhenX Core Tier 1 is a part of the Substance Abuse and Addiction Collections (<https://www.phenxtoolkit.org/sub-collections/view/8>) that are being adopted across NIDA-funded research. We are using the following subset of measures from the Core Tier 1: demographics (age, ethnicity, gender, race, current educational attainment, current employment status, and current marital status) and current substance use (tobacco, alcohol, and drugs) (Hamilton et al, 2011). The demographics (except for employment status) will only be collected at baseline, while current substance use and current employment status will be collected at baseline and follow-up.

11.3.5 PhenX Substance Abuse and Addiction Core Tier 2 (PhenX Core Tier 2)/National Survey on Drug Use and Health (NSDUH)

The PhenX Core Tier 2 (<https://www.phenxtoolkit.org/sub-collections/view/9>) is a complementary set of 8 measures to the PhenX Core Tier 1 (e.g., annual family income, child-reported parental education attainment, family history of substance use problems, household roster-relationships, internalizing, externalizing, and substance use disorders screener, occupation/occupational history, peer/partner substance use and tolerance of substance use, and social networks). We will only use a subset of questions from the Annual Family Income measure to get an estimate of total income of all family members (Hamilton et al, 2011). If the participant is unsure of the total family income, then we will use a subset of questions from the Substance Abuse and Mental Health Services Administration (SAMHSA)'s NSDUH survey to determine which income category best characterizes total combined family income (Center for Behavioral Health Statistics and Quality, 2017). Income will be collected at baseline only.

11.3.6 NetSCID-5

The Structured Clinical Interview for DSM-5 (SCID-5) is a semi-structured interview designed to assess substance use and mental health diagnoses (First et al, 2015). This study will use an electronic version of the SCID-5, the NetSCID-5, developed by TeleSage™. The TeleSage™ NetSCID-5 is fully licensed by the American Psychiatric Association and has been validated (Brodey, First, Linthicum, Haman, Sasiela, & Ayer, 2016). The NetSCID is HIPAA-compliant, and data is maintained on a secure, encrypted, and geo-redundant server. TeleSage™ has the capability of customizing the NetSCID-5 measure, so only modules relevant for this study will be selected (bipolar I disorder, major depressive disorder, panic disorder, social anxiety disorder, generalized anxiety disorder, posttraumatic stress disorder, adult attention deficit hyperactivity disorder, alcohol use disorder, cannabis, stimulants/cocaine, opioids, PCP, other hallucinogens, inhalants, sedative-hypnotic-anxiolytic, and other/unknown).

At the end of the study, all data collected on the TeleSage™ platform and stored on their server(s) will be securely transferred to Dartmouth's server and expunged from TeleSage™'s server(s).

11.3.7 Urine Drug Screen

Urine drug screen kits (UDS), otherwise referred to as urine toxicology, will be mailed to participants, and participants will be asked to collect a urine sample, record and upload results to study team using a secure system (e.g. REDCap). In rare cases when there are technological issues with uploading the photos, the participant can send photos to research staff via text to a research staff member's Kaiser cell phone (which is KPIT approved). In this case, research staff will upload the photographs into REDCap for the participant. All urine specimens are collected using CLIA-Waived and FDA-approved one-step multi-drug screen test cup following the manufacturer's recommended procedures. The study will use the DrugConfirm™ Advance Urine Drug Test Kit which screens for: alcohol, amphetamine, barbiturate, buprenorphine, benzodiazepine, cocaine, fentanyl, MDMA [ecstasy/molly], methamphetamine, methadone, morphine 300 ng/mL, oxycodone, phencyclidine (PCP), tramadol and THC.

11.4 Follow-up

11.4.1 Follow-up Assessment

The follow-up assessment will collect the following: current substance use (e.g., tobacco, alcohol, opioids, and other drugs), current employment status, participant experience with the study devices (including wearing the smartwatch, carrying the smartphone, and responding to EMAs), treatment utilization, reasons for drop out (if appropriate), insurance coverage, medication use/dose (if applicable), and overdose.

11.5 Digital Health Technology

11.5.1 Ambulatory Physiological Assessment using Mobile Sensors

We will develop a smartphone application, that can sense and store contextual information about a participant, e.g., location, physical activity (steps), phone activity (non-identified audio information such as segments of silence, speech features such as pitch control and voice quality), app usage, call/text, screen on/off, phone lock/unlock, sleep, ambient light, and proximity (e.g., to user's ear). Features will be derived from the raw sensing streams to create multiple relevant contextual variables. This application will be installed directly on the study provided smartphone (Moto G7 Power) or on a participant's smartphone (if they have a compatible phone). The data collected will be stored on the smartphone and will be securely transmitted to a secure cloud-based database hosted at Dartmouth.

In addition to the smartphone, the participants will be provided with a smartwatch (Garmin Vivosmart 4). The participants will be asked to wear the smartwatch continuously (except during pre-determined exceptions periods, such as when the participants are showering or charging the device). In our experience, the Garmin Vivosmart 4 smartwatch (among others) is comfortable, lightweight, and has a long battery life and an easy-to-use interface. The device can reliably track distance traveled, physical activity (including metrics of energy expenditure and step count), sleep stages, as well as heart rate. Data from the Garmin smartwatch includes raw sensor data, like, heart-rate, and several high-level features computed by Garmin (using their proprietary algorithms including; sleep stage information, periods of light/deep sleep, stress levels, and others). This data will be transmitted to the Garmin Connect application installed on the smartphone, which would in turn send the data to Garmin cloud servers. Garmin will provide us with access keys for the research staff to pull the data from the Garmin servers to the cloud-based database at Dartmouth College.

11.5.2 Ecological Momentary Assessment (EMA)

Participants will be prompted up to 3 times per day over 12 weeks by the smartphone app to self-report sleep, stress, pain severity, pain interference, pain catastrophizing, craving, withdrawal, substance use risk context, mood, context, substance use, self-regulation, MOUD adherence, and the impact of COVID-19 (Buysse, Reynolds, Monk, Berman, & Kupfer, 1989; Freeman & Gottfredson, 2018; Kuerbis et al., 2019; Preston et al., 2017, 2018). The EMA prompt delivery times will be randomized within each of the prompt timeframes (e.g., morning, mid-day, end of day). In addition to prompted EMAs, participants will be asked to self-initiate EMAs if substance use occurred (e.g., opioids, cocaine, or other stimulants). All EMA data collected via the smartphone will be securely transmitted to a secure cloud-based database housed in the Research Computing Department at Dartmouth College.

11.5.3 Momentary Self-Regulation Scale

This brief 12-item questionnaire assesses self-regulation on a momentary basis as individuals move through their lives (S. J. Kim et al., Under Review). This information will be collected up to 3 times daily over the 12-week study period by smartphone. All data collected via the smartphone will be securely transmitted to a secure cloud-based database housed in the Research Computing Department at Dartmouth College.

11.5.4 Social Media

Participants will be asked to download their social media data to a secure server using a remote desktop application. Images/texts of postings and comments as well as date/time and the number of reaction responses (e.g., Like, Sad, Angry) per posting and per comment will be extracted from the downloaded social media data through postprocessing for analysis. The download will occur at the beginning of the study and also at the end of the study. If participants have difficulty downloading the social media data, the research staff can provide guidance/instructions on how to download social media data and if needed can walk through the download process with the participant via phone or video. Should a technical issue arise that the research staff cannot resolve, research staff may need to contact technical support personnel at Dartmouth using a 3-way or conference call to assist with troubleshooting technical issues. All social media data will be securely stored on an encrypted server at the Williamson Translational Research Building in the Biomedical Data Science Department at Dartmouth College.

11.6 Other Measures

11.6.1 Electronic Health Records (EHR)

EHR data extraction will include all outpatient and inpatient encounters, medications (buprenorphine and others*), procedures, and diagnoses for the 12 months prior to EMA start and the 12-week study period. In addition, we will extract lab results from urine drug screens, patient demographic information, and insurance deductible level. We will extract appointment data to determine if visits were cancelled or missed. We will examine membership data to determine if the patient's membership became inactive in the study period. KPNC is an integrated healthcare delivery system, and the KPNC EHR includes both services provided inhouse and services obtained outside of KPNC, so long as the non-KPNC services were submitted as medical claims for reimbursement.

*Prescription data for opioids other than buprenorphine will be limited to patient-level dichotomous variables (yes/no) reflecting whether any non-buprenorphine opioid was ordered or dispensed during the time period.

11.7 Clinical and Safety Assessments

11.7.1 Safety Events

Safety events may be elicited at baseline or spontaneously reported to study staff at any visit following consent. Safety events suggesting medical or psychiatric deterioration will be brought to the attention of the Study Clinician for further evaluation and management. Safety events reporting are according to the reporting definitions and procedures outlined in the protocol and in accordance with applicable regulatory requirements. See Appendix A for details.

12.0 TRAINING REQUIREMENTS

12.1 Overall

A comprehensive Training Plan will be developed to incorporate general training, study-specific training, mechanisms for competency assessment as well as a detailed description of training, supervision, and fidelity monitoring procedures. The Investigative Team is responsible for the development of a comprehensive Training Plan, instructional material, and delivery of the training, with the team comprised of the Lead Node and other participating Nodes, and subject matter experts, as applicable. The Northeast Node is the Lead Node.

The CTN-0084-A2 study staff will be trained as specified in the study Training Plan. Training will include Human Subjects Protection (HSP) and Good Clinical Practice (GCP) as well as protocol-specific training on assessments, study interventions, safety and safety event reporting, study procedures, data management, quality assurance, laboratory procedures, etc. The Lead Node and Local Node are responsible for development and delivery of study-specific training related to the study intervention(s) and procedures including data management, as well as, non-intervention training (e.g., regulatory and laboratory procedures, safety and safety event reporting, quality assurance and monitoring, etc.). Other parties will contribute as needed based on the subject matter and material to be covered. The various sub-teams will collaborate to deliver quality instructional material designed to prepare research staff to fully perform study procedures based on the assigned research roles and responsibilities.

In addition to general and study-specific training, the Training Plan will include a description of the delivery methods to be used for each training module (e.g., via self-study, online, webcast, or teleconference). Study staff is required to complete institutionally required training per their research site, Institutional Review Board(s), and authorities with regulatory oversight. Tracking of training completion for individual staff as prescribed for assigned study role(s) will be documented, endorsed by the Lead Node. As changes occur in the prescribed training, the Training Plan and training documentation tracking forms will be amended to reflect these adjustments.

13.0 CONCOMITANT THERAPY/INTERVENTION

13.1 General

Not applicable for this study.

13.2 Medications Prohibited/Allowed During Trial

There will be no medications prohibited during the trial. Based on what we know about the population at the study site, participants will be receiving buprenorphine medications for substance use; psychiatric medications; and, medications for physical/medical ailments, in addition to behavioral treatments.

14.0 STATISTICAL DESIGN AND ANALYSES

14.1 General Design

14.1.1 Study Hypothesis

Feasibility of digital health technologies: The collection of intensive longitudinal data requires participants to adhere to wearing and carrying a smartwatch and smartphone, respectively, consistently throughout the study. Participants are also expected to respond to assessment questions up to 3 times a day and self-initiate EMA if substance use occurred, on every day of the 12-week study. We hypothesize that the financial incentives provided to participants will adequately incentivize these adherence behaviors.

Understanding behaviors of patients in treatment: We hypothesize that, intensive longitudinal data capturing of patient context and psychological state (via EMA) will be useful for predicting treatment retention, and buprenorphine medication adherence.

14.1.2 Primary and Secondary Outcomes (Endpoints)

The primary outcomes will include: (1) the percentage of days during the 12-week active phase enrolled participants wore/carried the smartwatch and smartphone; (2) response rate to EMA prompts during the 12-week phase; and (3) the percentage of participants who consent to social media data download and sparsity of social media data per participant.

The secondary outcome measures will be: (1) OUD treatment retention (days retained in OUD treatment program) based on EHR data; (2) Days covered on MOUD based on EHR and EMA data; and (3) Non-prescribed opioid use based on EHR and EMA data.

14.1.3 Recruitment

Participants will be recruited from Kaiser Permanente Northern California patients who have been treated at the KPNC AMRS programs for OUD.

14.1.4 Randomization and Factors for Stratification

Does not apply to this study.

14.2 Rationale for Sample Size and Statistical Power

14.2.1 Projected Number of Sites

We plan to recruit from Kaiser Permanente in Northern California (KPNC).

14.2.2 Projected Number of Participants per Site

Approximately 50 (if recruitment is faster than anticipated, we will recruit up to 75) participants are projected to be recruited from KPNC.

14.3 Statistical Methods for Primary and Secondary Outcomes

For our primary and secondary outcomes, we intend to use measures such as precision, recall (sensitivity) and specificity, F-score, to assess the quality of our predictions. The quality of the

identified digital phenotypes will be evaluated using cohesion (e.g., Silhouette score) and endpoint-differentiating power (e.g., Z-score).

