14.4 Significance Testing

The primary outcome will be evaluated using a two-sided test with a type I error rate of 5%. There are several secondary outcomes; however, multiple comparisons will not be adjusted for since these are not part of the study's primary objective as an observational study.

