1. *Explaining temporal-causal relationships between factors determined to be useful for predicting outcomes:* Although machine learning methods may often be more effective for prediction than simple regression or correlation, they may be difficult to explain, or may not reveal insights regarding the relationships between factors. Therefore, we also include a set of analyses that are conducive to generating such explanatory or descriptive insights. For example, we will apply supervised metric learning and prototypical case-based reasoning (Hsueh et al., 2018), topic-modeling (e.g., Latent Dirichlet Allocation) and causal inference methods (Cheng, Bahadori, & Liu, 2014; Kleinberg & Hripcsak, 2011).
2. *Outcome detection using passively collected digital health data:* We plan to measure drug use and medication non-adherence events via EMA, multiple times a day. Since EMA requires a level of active engagement from participants that may not be realistic to expect outside of a research study, we plan to use machine learning to detect these events using only passively collected data. The methods used here would be similar to the machine learning methods previously described for binary classification.
3. *Feasibility of digital health technology:* We will generate descriptive statistical summaries of the level of adherence of study participants to the desired protocol (e.g., EMA response rate, smartwatch and smartphone wear/carry rate). No statistical inference is planned for this assessment.

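### Section 14.3 names classification measures for primary feasibility outcomes that nothing predicts, 14.4 and 14.5 give two further and conflicting treatments, and the only workable one specifies neither an estimator nor an interval

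*Combined protocol and SAP*

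**What the plan says.** Section 14.1.2 (and 7.1) lists three primary outcomes:

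- Device use: "the percentage of days during the 12-week active phase enrolled participants wore/carried the smartwatch and smartphone".
- EMA: "response rate to EMA prompts during the 12-week phase".
- Social media: "the percentage of participants who consent to social media data download and sparsity of social media data per participant".

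Three places then say how they are to be analysed.

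- **14.3**, under a title that names both kinds of outcome, states: "For our primary and secondary outcomes, we intend to use measures such as precision, recall (sensitivity) and specificity, F-score". The rest of that sentence says the measures serve to judge how good the predictions are.
- **14.4**: "The primary outcome will be evaluated using a two-sided test with a type I error rate of 5"%. No test, null value or threshold is named.
- **14.5, item 3**: "We will generate descriptive statistical summaries of the level of adherence of study participants to the desired protocol". The item ends by ruling out inference: "No statistical inference is planned for this assessment". Section 2.6 says the same.

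No section mentions a confidence interval. The Extended Data Analytic Plan is cited in 14.7 for exploratory analysis only.

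**The concern.** Precision, recall, specificity and F-score all need a predicted class to set against an observed class. The primary outcomes have none. The prediction objective in 2.1 and 5.2 concerns treatment retention and buprenorphine adherence, and no section plans to predict wear days, EMA response or consent. The section that should state the primary method therefore states one that cannot be carried out.

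The other two treatments contradict each other: one plans a 5% test, the other no inference. Description is the only one that can be done as written. Even there, the plan leaves open whether a rate is averaged over people or pooled over prompts or days, and what measure of uncertainty goes with it.

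Section 2.4 says the results are meant to inform other HEAL studies and trials. Those users need to know how precise a feasibility rate from about 50 people in one health system is.

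**Working it through.** **1. Match each method to each primary outcome.**

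| Primary outcome | 14.3 classification measures | 14.4 two-sided 5% test | 14.5 item 3 / 2.6 description |
|---|---|---|---|
| Wear/carry days | No predicted class | No null value | Workable; unit and interval not stated |
| EMA response rate | No predicted class | No null value | Workable; unit and interval not stated |
| Consent percentage | No predicted class | No null value | Workable; interval not stated |
| Sparsity | No predicted class | No null value | Workable; summary not stated |

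Section 14.1.1 does not supply the null value. It hypothesises that the incentives will be adequate but sets no level of adherence.

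**2. The plan's own figure for N.** Section 9.2 expects about 180 patients approached and 30% recruited: 180 × 0.30 = 54, against a stated approximate 50 (up to 75). Both are given as approximate, so I read the gap as rounding. There is no power or precision calculation to reproduce.

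**3. Consent percentage.** The documents give no expected rate, so these are illustrations. Exact (Clopper-Pearson) 95% intervals:

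- 25/50 = 50%: 35.5% to 64.5%
- 40/50 = 80%: 66.3% to 90.0%
- 38/75 = 50.7%: 38.9% to 62.4%
- 60/75 = 80%: 69.2% to 88.4%

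**4. Per-participant or pooled.** Let participant i receive m_i prompts and answer a proportion r_i. The per-participant estimate is the mean of r_i. The pooled estimate is Σ m_i r_i / Σ m_i. They differ by Cov(m_i, r_i) / mean(m_i), so they agree only if response is uncorrelated with the number of prompts received. The plan gives reason to expect unequal m_i: prompts are up to 3 a day (11.5.2) and participants may withdraw (10.3). Non-engagers are also kept in the study (8.3), so low response rates will be in the data. The same algebra applies to wear/carry days if observed days differ between people.

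**5. Uncertainty in mean EMA response or wear/carry percentage.** Half-width = 1.96 × SD/√N. The between-person SD is my assumption: 20 to 30 points.

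- N = 50: 1.96 × 20/√50 = 5.5 points; 1.96 × 30/√50 = 8.3 points. The t quantile gives 5.7 and 8.5.
- N = 75: 1.96 × 20/√75 = 4.5 points; 1.96 × 30/√75 = 6.8 points.

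**6. Why the unit matters for any interval.** The maximum number of prompts at N = 50 is 50 × 84 × 3 = 12,600. If all were treated as independent at an assumed 70% rate, the half-width would be 1.96 × √(0.7 × 0.3/12,600) = 0.8 points. With 252 prompts per person the design effect is 1 + 251 × ICC, which is 26.1 at ICC 0.1 and 126.5 at ICC 0.5. The half-width becomes 0.8 × √26.1 = 4.1 and 0.8 × √126.5 = 9.0 points. The ICC range is also an assumption.

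**The case against.** The strongest reply is that 14.3 contains a drafting slip and nothing more. Its sentence ties the measures to the quality of predictions, prediction is the secondary objective, and 14.5 lists the same measures under prediction. The feasibility method is stated twice, in 2.6 and 14.5, and no analyst is likely to compute an F-score for a consent percentage. I accept that the slip is the likely explanation. The title and sentence of 14.3 still include the primary outcomes, and correcting them leaves the conflict between 14.4 and 14.5 in place.

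A second reply is that leaving out inference is a declared choice: the synopsis calls the study a pilot without power for hypothesis tests. That stands as an argument against the test in 14.4. It is not an argument against a descriptive interval. A reader given the consent count and N could compute that interval unaided, but not the intervals for wear days and EMA response, which need the spread between people.

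Two stronger readings are tempting.

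- A reader might infer that the primary results will be bare percentages. The documents do not say so. Descriptive summaries can include spread, and 14.9 gives medians, quartiles, means and SDs for continuous baseline variables. What can be said is that no measure of uncertainty is specified for the primary outcomes.
- A reader might infer that the study will report falsely narrow intervals by counting prompts as independent. The plan contains no such analysis. The contrast in step 6 rests on an assumed rate, an assumed ICC and the maximum prompt count, so it is a reason to fix the unit in advance and not a predicted error.

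**Conclusion.** The point holds as a defect in the specification of the primary analysis. Section 14.3 assigns measures that cannot be computed for the primary outcomes, 14.4 and 14.5 disagree about testing, and the workable descriptive method leaves its unit and its measure of uncertainty unstated.

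The uncertainty left unspecified is material. At 25/50 the exact interval for consent runs about 14 to 15 points either side; at 38/75 it runs about 12. These are near the widest case, since rates further from 50% give narrower intervals. For mean EMA response at N = 50 the half-width is about 5.5 to 8.3 points, conditional on the assumed SD of 20 to 30 points. Enrolled N may exceed 50, because 8.3 sets the target in engaged participants and keeps the others.

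A reader might infer that the primary result is invalid. The documents do not support that, since the descriptive summaries can be produced as planned. This is a wording repair plus a better reporting method, cheap enough to be worth making.

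**What to change.** - **14.3:** remove the primary outcomes from the sentence, and limit the classification measures to binary or dichotomised secondary and other predicted endpoints. Removing the primary outcomes alone is not enough, because secondary outcomes 1 and 2 in 7.2 are day counts.
- **14.4:** delete the test of the primary outcome.
- **14.5 item 3 and 2.6:** replace the statement that no inference is planned with: no hypothesis test is planned; 95% intervals are descriptive.
- **Wear/carry days and EMA response:** compute each per participant among all enrolled, non-engagers included. Report mean and median with a 95% interval from resampling participants.
- **Consent percentage:** report with an exact binomial 95% interval.
- **Sparsity:** report as a per-participant distribution (median and quartiles).

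The cost is SAP wording and a little analysis work, with no new data or participants. The downside is that the feasibility rates will carry visibly wide intervals.
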